Atopic dermatitis, commonly called eczema, is one of the most frequently occurring skin conditions. It is estimated to affect around one fifth of children in developed countries and is also becoming increasingly common in less developed countries. Exact estimates of how common eczema actually is, vary considerably and there has not been an in-depth analysis of the number of people with eczema in the UK. It is also unclear which groups of people are most affected and which treatment options are being used.

Most people with eczema are managed by their GP with only a few people requiring specialist care. GP records therefore provide an excellent opportunity to explore how common eczema is and which treatments are being used currently. Through these studies we aim to provide accurate estimates of the number of people with current eczema (prevalence), number developing new onset eczema (incidence), and the pattern of common comorbidities in people with eczema. We also aim describe current treatment patterns by age groups and other factors. We will look back over the last decade to identify how the number of people with eczema and treatments changing over time. We will also explore patterns in the people most commonly affected and in the treatments used.

Introduction

Atopic dermatitis (AD), also known as atopic eczema, is a chronic inflammatory skin condition which affects around 200 million people worldwide.¹ It most commonly develops in the first year of life although the onset can occur at any age.^{2,3} AD usually often follows a relapsing-remitting course and remission may require the use of maintenance therapies.⁴ Whilst the majority of affected children will have resolution or improvement by late childhood,² a substantial proportion of people will have ongoing AD into adulthood and flares can occur even after long periods of remission.^{3,5} AD can be extremely disabling and can have a significant psychological impact in both children and adults⁶⁻⁸ and it has been estimated that around 30% of AD is moderate or severe.⁹ The current treatment approach involves avoidance of individual trigger factors, the application of emollients, and a multistep approach to the use of anti-inflammatories depending on disease severity.⁴

In the UK prevalence estimates vary widely, especially in adults. Recent questionnaire-based studies suggest wide ranging prevalence rates of 2.5-15%.^{10,11} Given that 97% of AD patients are seen and treated in principally in primary care in the UK, databases of electronic health records from GP practices provide a rich data source from which epidemiological analyses can be derived.¹² Using the UK Clinical Practice Research Datalink (CPRD), approximately 500,000 people were identified as having AD between 1998-2015 which scales to an approximate UK prevalence of 10%.¹³ However, the limitation of this study is that it was originally designed to assess cardiovascular outcomes in AD not prevalence per se and only assessed the adult population. Incidence rates of eczema have been recently described in the UK to 2015, but only in children.^{14,15}

AD is associated with a wide range of comorbidities. Children with AD are at increased risk of asthma and allergic rhinitis,² and depression is more common in both children and adults.⁸ Severe and active AD was also demonstrated to be a risk factor for incident cardiovascular disease in a recent UK primary study,¹³ and an association with an increased risk of new-onset rheumatoid arthritis and inflammatory bowel disease, but a decreased risk of type 1 diabetes,

has been observed in population data.¹⁶ However, high quality data on the overall pattern of comorbidity in individuals with AD are lacking.¹⁷

The burden of management falls largely on primary care in the UK with 97% of people with AD seen and treated primarily by their GP.¹² Attendance rates are also high with 96% children with AD reported to have had a primary care attendance within the preceding year.¹⁸ It has been estimated that 16-30% of AD is moderate or severe,^{9,18} and whilst those with more severe disease are more likely to be referred for specialist care, the majority of these cases are still managed without secondary care referral.¹⁸ The most significant monetary costs for AD are also due to primary care attendances and prescribing.¹⁹ Despite this high disease burden of AD a contemporary overview of healthcare and treatment utilisation in children and adults with AD in the UK is currently lacking.

Aims

In these retrospective cohort studies, we aim to describe:

1. The incidence and prevalence of AD in primary care in children and adults, including variation by sociodemographic factors and calendar year.
2. Patterns of possible AD-associated comorbidity post-diagnosis.
3. Prescribing patterns for individuals with AD, and how prescribing varies by sociodemographic factors and calendar time.
4. Patterns of treatment escalation in individuals with AD.

Methods

Study design and population

We aim to perform a retrospective cohort study using the Royal College of General Practitioners Research and Surveillance Centre (RCGP RSC) database. All adults and children of any age contributing data to the RCGP RCS database between January 1, 2008 and January 1, 2018 for at least one year, will be eligible for inclusion in the study.

Treatments for AD are also used to treat other conditions and the indication from treatment is not readily available from large datasets in the UK. We will therefore exclude people with potential confounding comorbidities from our AD cohort when assessing treatment utilisation. We will exclude people with skin conditions also excluded by Abuabara et al.²⁰ (psoriasis, contact dermatitis, photodermatitis, and ichthyosis), those with inflammatory bowel disease (IBD), or rheumatoid arthritis, and those with a history of organ transplantation. IBD and rheumatoid arthritis will be identified using approaches validated in UK primary care databases and previously described.²¹⁻²³ In the absence of a validated method to identify the presence of organ transplantation from routine UK primary care data, this will be identified using a Read code list generated in accordance with published guidance.^{24,25}

Atopic dermatitis definition

Individuals with AD will be identified using a validated algorithm developed for use with the UK electronic health record,²⁰ and used in recent UK studies in AD.^{13,14} The positive predictive value of this algorithm is 90% (95% Confidence interval (CI) 80-91%) in children and 82% (95% CI 73- 89%) in adults.²⁰ In brief, AD is identified by the presence of one diagnostic code and with at least two eczema-related treatment codes on separate days within three months before or one year after the diagnostic code.

AD severity will be defined using the approach used by Silverwood et al. in their study of cardiovascular outcomes in AD:¹³ AD will be considered moderate at the prescription of a second potent topical corticosteroid treatment within one year or a first topical calcineurin inhibitor (TCI). AD will be considered severe at the first of a systemic immunosuppressant treatment, phototherapy, or a dermatology referral.

Active AD has been defined from electronic health records in a recent study as: The onset of active AD was defined as the later of two AD records appearing within any one year period.¹³ Active AD was then assumed to last for one year, unless another AD record appeared in which case its duration was be prolonged for a further one year period.¹³ We will utilise this approach

but use the first of two codes (rather than the latter) within one year to signify the onset of active AD, as this has been shown to have good agreement to physician confirmed onset.²⁰

Primary care visits and specialist referrals definitions

A primary care visit for AD will be defined as any primary care attendance associated with either a diagnostic code for AD or a prescription for one or more AD treatments. Specialist referrals will be identified by the presence of a Read code for referral to; a dermatologist, a GP with a specialty interest in dermatology, or dermatology specialist nurse.

Definition of baseline variables

Age will be initially grouped in accordance with trial data reporting, as follows: 0-1, 2-6, 7-11, 12-17, 18-29, 30-39, 40-49, 50-59, 60-69, 70-79, >80 years. To examine how disease incidence varies across other sociodemographic factors stratified by age at diagnosis we will also define broader age groups. Ethnicity will be categorised as follows using a previously described informatics ontology for ethnicity and using the major UK census categories:^{26,27} White, Asian, Black African/Caribbean, Mixed, Other, or not reported.

Deprivation will be defined based using the official national deprivation measure; index of multiple deprivation (IMD).²⁸ IMD is calculated based on patient postcode at the point of data extraction. Scores will be divided into quintiles based on the national distribution of IMD scores.

Other factors included for analysis comprise; smoking status, alcohol use, concomitant atopic diseases, depression, family history of atopy, biomarkers and laboratory test, and other comorbidities.

Definition of atopic dermatitis-associated conditions

AD-associated conditions considered will comprise: asthma, allergic rhinitis, depression, anxiety, other psychological disorders, rheumatoid arthritis, inflammatory bowel disease, coeliac disease, type 1 diabetes, multiple sclerosis, and alopecia.

Atopic dermatitis treatments

least one year follow-up prior to the diagnosis date will be required to confirm the diagnosis was incident. Individuals with a diagnosis within one year of registering with a practice will be excluded from the incident analysis, unless under one year old. Age-standardised incidence rates (per 100 person-years), stratified by age, other sociodemographic factors and calendar year, will be calculated by dividing the number of incident patients by the sum of person-years of follow-up for the total eligible population over the study period. Adjusted incidence rate ratios by sociodemographic factors will be estimated using Poisson regression.

In the incident cohort with AD we will examine disease trajectories by describing the proportion of individuals who developed moderate and severe AD post-diagnosis. We will evaluate the impact of sociodemographic predictors on time to first occurrence of moderate and severe AD using Cox proportional hazards models. Time to return to active AD will also be evaluated in the subset of individuals whose disease was defined as active at diagnosis using the same approach.

AD-associated conditions

In the prevalent cohort we will describe the prevalence of AD-associated comorbidities in all individuals at the start of follow-up. Start of follow-up for an individual with AD will be defined as the latest of: 1 Jan 2008, the date of diagnosis of AD, or 365 days after practice registration. Prevalence estimates will be compared to those of a matched unexposed cohort without AD. The matched unexposed cohort will be defined by matching individuals in the exposed cohort with individuals without a diagnosis of AD, by age and sex at GP practice level. The start of follow-up for each matched individual will be the start of follow-up of their matched counterpart. Unexposed individuals will be required to have at least one year of follow-up in RCGP RCS when matched to minimise the risk they have a non-recorded existing diagnosis of AD.

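### Severe AD can be triggered by a dermatology referral alone, so its sociodemographic hazard ratios mix disease severity with referral behaviour

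*Combined protocol and SAP*

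**What the plan says.** The Incidence section, in its paragraph on disease trajectories, sets the analysis: "We will evaluate the impact of sociodemographic predictors on time to first occurrence of moderate and severe AD using Cox proportional hazards models".

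The outcomes are defined under Atopic dermatitis definition. For severe disease: "AD will be considered severe at the first of a systemic immunosuppressant treatment, phototherapy, or a dermatology referral". Any one of the three is sufficient. For moderate disease: "AD will be considered moderate at the prescription of a second potent topical corticosteroid treatment within one year or a first topical calcineurin inhibitor". That definition rests on prescriptions only.

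The section defining primary care visits and specialist referrals explains how a referral is found: "Specialist referrals will be identified by the presence of a Read code for referral to; a dermatologist", with GPs who have a dermatology interest and dermatology nurses also included. It does not require the referral to be for AD. The exclusion of psoriasis, contact dermatitis and other confounding conditions, under Study design and population, is stated for the assessment of treatment utilisation. It is not stated for the trajectory analysis.

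The Introduction says two things about referral in moderate or severe disease: "those with more severe disease are more likely to be referred for specialist care", but "the majority of these cases are still managed without secondary care referral".

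The Abstract lists specialist referrals, stratified by sociodemographic factors, as part of healthcare use. Secondary analyses are described in general terms, and none is named for the severity definition.

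**The concern.** A referral records a decision about care. Severity influences it, but so may help-seeking, local services and GP practice. If any of these differ between deprivation or ethnic groups at the same severity, the time to severe AD differs between groups for a reason other than disease. The plan itself treats referral as healthcare use in one place and as a severity event in another, against the same kind of predictor.

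At stake is how the hazard ratios are read. They sit under disease trajectories, so a ratio near or below 1 for a disadvantaged group invites the conclusion that its disease progresses no faster. The same ratio could arise from equal or worse disease with fewer referrals, and the composite alone cannot separate the two. A referral for another skin problem could also count, because no AD link is required.

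**Working it through.** **What can be reproduced.** The plan gives no event count, expected hazard ratio or power for this analysis, so there is no stated figure to check. What follows shows how far the composite could move under stated assumptions.

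**Consistency of the Introduction.** It gives "It has been estimated that 16-30% of AD is moderate or severe" and "97% of people with AD seen and treated primarily by their GP". If the remaining 3% were all moderate or severe, they would be 3/30 = 10% to 3/16 = 19% of moderate or severe cases. Being treated mainly by a GP is not the same as never being referred, so this is only a rough check. It agrees with the statement that most such cases are not referred.

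**Model.** Let t be the true hazard ratio for severe disease and s the share of severe events in the reference group that arise only through referral. Let r be the ratio of referral probabilities between the groups at equal severity. Access to systemic treatment and phototherapy is taken as equal. Then

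composite HR ≈ t × [s × r + (1 − s)].

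The values of t, s and r are all assumptions. At t = 1.2 and r = 0.7:

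- s = 0.3: 1.2 × (0.21 + 0.70) = 1.09
- s = 0.5: 1.2 × (0.35 + 0.50) = 1.02
- s = 0.9: 1.2 × (0.63 + 0.10) = 0.88

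Over a wider range, with t = 1.2:

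| s | r = 0.9 | r = 0.8 | r = 0.7 | r = 0.6 |
|---|---|---|---|---|
| 0.3 | 1.16 | 1.13 | 1.09 | 1.06 |
| 0.5 | 1.14 | 1.08 | 1.02 | 0.96 |
| 0.9 | 1.09 | 0.98 | 0.88 | 0.77 |

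With no true difference (t = 1.0), s = 0.9 and r = 0.8 give 0.72 + 0.10 = 0.82, a spurious association.

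**When the direction reverses.** The composite falls below 1 when r < [1/t − (1 − s)]/s:

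| s | t = 1.2 | t = 1.5 | t = 2.0 |
|---|---|---|---|
| 0.3 | r < 0.44 | impossible | impossible |
| 0.5 | r < 0.67 | r < 0.33 | impossible |
| 0.9 | r < 0.81 | r < 0.63 | r < 0.44 |

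**Simulation check.** Two groups with exponential onset were followed for 5 years, with a latent severe hazard of 0.04 per year in the reference group. The probability of referral there was 0.45 and of the other route 0.05. This implies s = 0.45 × 0.95 / (1 − 0.55 × 0.95) = 0.90. The crude event-rate ratios were:

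| True HR | r = 1 | r = 0.8 | r = 0.67 | r = 0.5 |
|---|---|---|---|---|
| 1.2 | 1.18 | 0.97 | 0.81 | 0.65 |
| 1.5 | 1.45 | 1.17 | 1.01 | 0.78 |

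The formula at s = 0.9 and t = 1.2 gives 0.98 at r = 0.8 and 0.66 at r = 0.5, close to the simulated 0.97 and 0.65.

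**Referrals not for AD.** If these occur at the same rate in both groups, at b times the reference group's severe hazard, the ratio becomes (t + b)/(1 + b). With b = 1, a true 1.5 becomes 2.5/2 = 1.25 and a true 1.2 becomes 2.2/2 = 1.10. This pulls the result towards 1 even when r = 1.

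**The case against.** The case for leaving the plan as it is has real weight.

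- The documents do not say that referral dominates the severe events. Oral steroids appear among the oral systemic treatments, and if they count as systemic immunosuppressants the referral share could be much lower. Nor does any passage say that referral differs by deprivation or ethnicity at equal severity. Both objections stand, so the size of the effect is unknown.
- The Introduction says that worse disease is referred more often, which supports referral as a marker of severity. Its remark about non-referral concerns moderate and severe disease together and secondary care only, whereas the plan's referral code set is wider. This also stands: low referral in the pooled group does not establish how sensitive referral is for severe disease.
- The definition is declared openly and taken from a published UK study, which helps comparability. That is a reason to keep the composite. However, the plan describes that study as one of cardiovascular outcomes, and it quotes validation figures for identifying AD but none for severity.
- Referrals and prescribing by class will already be described by sociodemographic factors. These summaries help, but the prescribing rates are annual figures in the prevalent population. They do not break down a time-to-event outcome in the incident cohort.

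A reader might infer that the hazard ratios simply measure access to care, that most moderate or severe patients are never referred, or that reversal should be expected. The documents support none of these. Referral tracks severity in part, being managed without secondary care referral is a weaker statement than never being referred, and reversal needs particular values of s and r.

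**Conclusion.** The concern holds for severe AD only. Because referral alone can trigger the outcome and need not relate to AD, the sociodemographic hazard ratios combine severity with referral behaviour, and no planned analysis separates them.

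The size is conditional. For a modest true hazard ratio of 1.2, the illustrated cases run from slight attenuation (1.16 at s = 0.3, r = 0.9) to reversal (0.77 at s = 0.9, r = 0.6). For a true ratio of 2.0, reversal is impossible at a referral share of 50% or less. These results assume equal access to systemic treatment and phototherapy, and the values of s and r are illustrative. That s is unknown is itself a reason to report it.

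**What to change.** Keep the published composite for comparability and add two Cox models in the incident cohort:

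- (a) time to first systemic immunosuppressant or phototherapy, whether or not a referral came earlier;
- (b) time to first dermatology referral, labelled as healthcare utilisation.

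Count only referrals linked to an AD record where the data allow. Report the share of severe events that were referral only, overall and by sociodemographic group, and state which drug classes count as systemic immunosuppressants for this outcome. Call the composite treatment- or referral-defined severity, and do not read its sociodemographic hazard ratios as disease progression without the component results beside them.

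Agreement between (a) and (b) should not be made a condition for drawing conclusions. Limited access can lower both, and they would then agree on a biased answer.

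The cost is two extra models on existing data, plus the work of linking referrals to AD records. Outcome (a) will have fewer events and less precision. It still depends partly on specialist access, so it removes the referral trigger but is not free of access effects.

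### AD cases must have recorded practice contact and their matched comparators need not, so the comorbidity comparisons risk differential ascertainment that no planned analysis checks

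*Combined protocol and SAP*

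**What the plan says.** Under Methods, Atopic dermatitis definition, "AD is identified by the presence of one diagnostic code and with at least two eczema-related treatment codes on separate days". The treatment codes may lie anywhere from three months ahead of the diagnostic code to a year beyond it.

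Under Statistical Analyses, AD-associated conditions, follow-up of an AD patient starts at the "latest of: 1 Jan 2008, the date of diagnosis of AD, or 365 days after practice registration". Comparators have no AD diagnosis, are matched "by age and sex at GP practice level", and take the start date of their AD counterpart. Their remaining condition is "Unexposed individuals will be required to have at least one year of follow-up in RCGP RCS when matched to minimise the risk" that "they have a non-recorded existing diagnosis of AD". No consultation or prescription is asked of them.

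Two comparisons follow. At baseline, "Prevalence estimates will be compared to those of a matched unexposed cohort without AD", for the full list of associated conditions and with no adjustment stated. For new-onset disease, Cox models cover rheumatoid arthritis, inflammatory bowel disease, coeliac disease, type 1 diabetes and multiple sclerosis. Their named adjustment groups are disease duration, sociodemographic factors, clinical measures and comorbidities. Anyone with a single day of follow-up is included, and there is no lag period. The Secondary analyses section provides for sensitivity analyses as needed and ties them to findings that were not expected; none is named.

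**The concern.** The two arms meet a similar registration condition but not a similar contact condition. Where the diagnosis date sets the start of follow-up, the AD patient has a coded contact on that day, and the qualifying prescriptions fall in the three months before it or the year after it. The comparator may be registered for the whole preceding year without being seen. A practice that has not seen a person has had little chance to record AD, which is what the one-year rule is meant to guard against, or to record a comorbidity.

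If recording depends on contact, the AD arm will show more recorded disease at baseline and earlier detection after it, even with no true difference. Comorbidity after diagnosis is a stated aim. The Introduction already expects more depression, rheumatoid arthritis and inflammatory bowel disease in AD, so an upward-biased result for these would look expected and might prompt no sensitivity analysis.

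**Working it through.** The plan gives no expected ratio, event count or power for these comparisons, so there is no figure of its own to reproduce. The check asks how large a ratio unequal contact could produce when the true ratio is 1.00.

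**Inputs**
- From the Introduction: "96% children with AD reported to have had a primary care attendance within the preceding year". This figure is for children; using it for all ages is an assumption.
- Assumed, because the documents give no figure: yearly attendance *a* among people without AD of 0.90, 0.80 or 0.70.
- Assumed detection. Extreme case: a condition is recorded only if the person attended. Mild case: it is recorded with probability 0.90 if the person attended and 0.70 if not.
- Assumed: no false-positive codes, and outcomes rare enough that the same factor approximates the effect on a hazard ratio.

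**Formula.** Observed ratio = true ratio × D(0.96) / D(*a*), where D is the probability of being recorded. In the extreme case D(*a*) is proportional to *a*. In the mild case D(*a*) = 0.90*a* + 0.70(1 − *a*) = 0.70 + 0.20*a*, so D(0.96) = 0.892.

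| Unexposed attendance | Extreme case | Mild case |
|---|---|---|
| 0.90 | 0.96/0.90 = 1.07 | 0.892/0.880 = 1.01 |
| 0.80 | 0.96/0.80 = 1.20 | 0.892/0.860 = 1.04 |
| 0.70 | 0.96/0.70 = 1.37 | 0.892/0.840 = 1.06 |

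If unexposed attendance were also 0.96, both columns would give 1.00.

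**An inverse association.** Take a true ratio of 0.70 for type 1 diabetes (assumed; the background gives the direction only). The largest mild factor gives 0.70 × 1.06 = 0.74, and the largest extreme factor gives 0.70 × 1.37 = 0.96. The association is pulled towards 1.

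**Whether a small ratio matters.** With equal arms and a two-sided 5% test (both assumed), the chance that a spurious hazard ratio is significant with *d* events is about Φ(√(*d*/4) × ln HR − 1.96). For HR 1.06, ln HR = 0.0583:
- *d* = 1,000: 15.81 × 0.0583 − 1.96 = −1.04, or 15%.
- *d* = 5,000: 35.36 × 0.0583 − 1.96 = 0.10, or 54%.

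The event counts are illustrative.

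**One arm or both.** Requiring a prior-year contact of the unexposed alone would give 0.892/0.900 = 0.99 in the mild case and 0.96/1.00 = 0.96 in the extreme case when the truth is 1.00. Requiring it of both arms gives 1.00.

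**The case against.** The strongest reply is that the arms are closer than they look and that the bias need not run one way.

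- *Registration is balanced.* The AD arm has its own 365-day condition, and matching within practice removes differences in recording between practices. This stands; the imbalance is in contact only.
- *AD contact need not be recent, nor all before entry.* A patient diagnosed well before 2008 can start follow-up with no visit near that date, and both treatment codes may come after the diagnosis that sets entry. So it is wrong to infer that every AD patient has consulted and been prescribed for just before follow-up starts. The timing argument applies to new cases.
- *Direction varies.* Better ascertainment before baseline removes existing disease from the AD new-onset analysis, while undiagnosed cases among the unexposed may later count as new onset and lower the hazard ratio. Unrecorded AD among the unexposed would normally pull associations towards the null. Both points stand.
- *Scope.* Depression, anxiety and allergic rhinitis, which may depend most on attendance, appear only in the baseline comparison. That susceptibility differs by condition is a judgement; the documents do not say so.
- *Existing safeguards.* Clinical measures and comorbidities may partly stand in for contact, but only in the Cox models, and they are themselves recorded largely through contact. The sensitivity clause also mentions corroboration, yet it commits to no analysis of this problem.

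A reader might infer that the planned associations will be inflated, or that 1.37 estimates by how much. The documents support neither: they contain no attendance figure for people without AD and no detection probabilities.

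**Conclusion.** The contact asymmetry follows from the cohort definitions, and nothing in the plan addresses it directly. It creates a risk of differential ascertainment, not a demonstrated inflation. Upward bias is the likelier direction for baseline prevalence and early new-onset hazard ratios, with masking for type 1 diabetes. The figures of 1.01-1.06 and 1.07-1.37 are conditional on assumed attendance of 70-90%, on a child attendance figure applied to all ages, and on the two detection models. The upper range is an extreme case, since long-standing diagnoses stay on the record, and the true effect could be near zero for conditions diagnosed regardless of AD visits. The check should nevertheless be prespecified, because in a large database even a small spurious ratio can reach significance.

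**What to change.** Keep the main analysis. Add to AD-associated conditions, as prespecified sensitivity analyses:

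1. Repeat the prevalence and Cox comparisons with **both** arms restricted to people with at least one primary care contact in the 12 months before the start of follow-up. Count only contacts before the start date, since otherwise the diagnosis visit would qualify every new AD case. Apply the restriction before matching, so that matched sets stay intact.
2. Fit a sensitivity Cox model that adds the number of contacts in those 12 months, because one or more contacts does not mean equal contact.
3. Repeat the new-onset models leaving out events and follow-up in the first year in both arms. This removes the period in which qualifying AD contact, and the late recording of existing disease, are most concentrated.

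Report for each condition whether the association persists.

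The cost is one further matched comparison and a few models on the same primary care records, published as an amendment with its rationale, as the protocol already provides. The downside is that attenders are sicker than the general population, and contact counts may partly reflect the comorbidity itself. These analyses may therefore understate associations and should sit beside the main analysis, not replace it. They also leave unequal contact later in follow-up, which should be stated as a limitation.
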